### 1. Introduction

Stand & Move at Work is a two-arm group-randomized trial. Worksites (N = 24) of small to moderate size (20–50 employees enrolled; N=720 employees across the 24 sites) will be randomized to one of two interventions: (a) *MOVE+*, a multi-level behavioral intervention targeting increases in LPA at the worksite; or (b) *STAND+*, the multi-level *MOVE+* intervention along with the installation of sit-stand workstations to allow workers to stand at their desks while working. Both worksite interventions are expected to reduce sitting and increase LPA over 12 months and improve cardiometabolic risk and work performance outcomes. We hypothesize the effects to favor the *STAND+* study arm because the additional sit-stand workstation enhancement will provide a robust environmental stimulus to reduce sitting and provide a unique catalyst for LPA in the workplace. The *MOVE+* arm will receive sit-stand workstations at 12 months and both arms will be assessed for follow-up at 24 months.

#### Primary Aim:

To evaluate the relative efficacy of *MOVE* and *STAND+MOVE* interventions on LPA and sitting behaviors over 12 months, with process measures at 3 months and maintenance measures at 24 months. The *STAND+MOVE* intervention, relative to the *MOVE* intervention, will: (H1) increase LPA at work and (H2) reduce sitting time at work over 12 months. Additional process outcomes at 3 months and maintenance outcomes at 24 months will be collected.

#### Secondary Aims:

To evaluate the relative efficacy of *MOVE* and *STAND+MOVE* interventions on cardiometabolic risk (composite measure of fasting glucose, insulin, triglycerides, HDL-cholesterol, and blood pressure) over 12 months, with additional follow-up to 24 months. The *STAND+MOVE* intervention, relative to the *MOVE* intervention, will (H3) lower cardiometabolic risk over 12 months

### 2. Study Organization

The study was funded by the National Cancer Institute at the National Institutes of Health. The trial is managed collaboratively by the Principal Investigators (PI) at both study sites (i.e. Arizona State University and the University of Minnesota, Twin Cities).

#### 2.1 Study Setting

Worksites will be enrolled in the greater Phoenix, AZ, USA and Minneapolis, MN, USA metropolitan regions. Twelve worksites will be randomized in each region. Selected worksites will be drawn from three distinct work sectors: higher education, industry/healthcare (e.g., law firms, health insurance providers), and government (e.g., state departments). Worksites will be equally selected in each sector across each region (n= 4/sector/region worksites).

Each site will be responsible for recruiting participating worksites and participating individuals within the worksties. A single digit site ID will be incorporated as the first digit of the three digit worksite ID that each enrolling worksite will be assigned.

#### 2.2 Study Site Teams

The PI of each site will be responsible for his own staff and will secure IRB approval prior to the start of the study team. A research coordinator at each site will work with the PI to ensure the study stays on the scheduled timeline, and that data collection and study activities are implemented according to study protocols.

### 3. Training and Documentation

All staff will complete IRB-required training, including human subjects, in advance of the study. In addition, all data collection staff will be trained on the collection of anthropometric and blood pressure measures. Phlebotomists collecting biospecimens (i.e. venous blood samples) will have completed all necessary training for the collection and handling of biospecimens.

### 4. Worksite Enrollment Process

The worksite enrollment process refers to the tasks that each site undertakes to initiate Worksite accrual, beginning with identifying potential worksites, screening and consenting, and randomizing.

#### 4.1. Identifying Potential Worksites

We will recruit worksites that meet our inclusion criteria and then recruit individual employees within each of the worksites (see Section 5). We aim to recruit 24 small to moderate sized worksites across our two geographical areas – Phoenix, AZ and Minneapolis/St. Paul, MN (12 worksites in Arizona and 12 in Minnesota; see inclusion criteria in Section 4.3). Partnerships with large companies from our preliminary studies will be leveraged to help identify participating worksites, although we will avoid recruiting individual worksites that have been involved in our past studies. We will also leverage others in our professional networks, including individuals involved in workplace wellness, to help identify potential worksites. In advance of the grant proposal, we garnered very strong and broad support from many employers and worksites of various sizes in both Arizona and Minnesota. We will be recruiting worksites from three different workplace sectors including academia, government, and healthcare to enable greater generalizability of study results.

#### 4.2. Timeline

Participating worksites will be recruited as pairs within a single sector at each worksite utilizing a rolling recruitment method. We will also rotate the enrollment of sector pairs over the seasons of the full calendar year to help avoid seasonal effects, beginning with the first two pairs enrolled in January 2016 and the final two pairs enrolled in November 2016. Enrolling two pairs every other month will also alleviate logistical and labor burdens for recruitment, data collection, and intervention implementation.

#### 4.3. Worksite-level Inclusion Criteria

Worksite level inclusion criteria include:

- (a) Size: small to moderate size worksite (20-60 employees)
- (b) Schedule: >80% of employees full-time

- (c) Occupation: seated office work, primarily computer- and telephone-based work, little movement or walking
- (d) Wellness environment: not currently undergoing a wellness program aimed at increasing activity at work
- (e) Workstations: willing to have sit-stand workstations installed at worksite
- (f) Willing to engage in worksite-level intervention activities
- (g) Willing to be randomized to either intervention condition

#### **4.4. Screening**

Worksites will be screened for eligibility by study questionnaires completed by worksite leadership and followed up with interviews by study personnel to verify eligibility. If a worksite meets the inclusion criteria, a general level of employee enthusiasm for the study will be assessed (see Section 4.4)

#### **4.5. Employee Interest Survey**

At worksites where inclusion criteria have been met, an anonymous survey will be sent to employees to gauge interest in participating in a study looking to decrease sitting time and increase light-intensity activity at work (i.e. level of enthusiasm and likely participation), and additional questions to assess both their physical workspace (whether the space could accommodate sit-stand desks) and individual level questions (to determine generally whether the person would meet the individual level inclusion criteria).

#### **4.6. Memorandum of Understanding/Agreement to Participate**

Presuming a worksite has enough employee interest to move forward, a memorandum of understanding will be developed and signed by the worksite manager and study principal investigators to facilitate adherence to the study timeline and intervention. As part of this process, both a study leader and study advocate(s) will be identified.

### **5. Participant Enrollment Process**

This section details Participant enrollment, beginning with recruitment, screening and consenting, and randomizing.

#### **5.1. Town Hall Presentations**

All worksite employees will be invited to a Town Hall presentation(s) scheduled based on the suggestions of the worksite leader and/or advocates. Up to two town halls will be scheduled at any given worksite to allow for the greatest attendance. While in-person Town Halls are desired, electronic town halls will be made available as an option. For those unable to attend a Town Hall, a copy of the TownHall powerpoint presentation will also be provided. The purpose of the Town Hall meeting will be to allow the site PI to state the study goals, aims, methods, inclusion/exclusion criteria, and timeline. Following the town hall, interested (or all, depending upon the preference of the worksite leader) employees will be emailed a description of the study, including a consent form, along with a link to complete the eligibility screener questionnaire.

### 5.2. Participant-level Inclusion Criteria

Participant eligibility criteria will be as follows:

- (a) 18 years or older;
- (b) generally good health and able to safely reduce sitting and increase LPA;
- (c) working full-time on-site (i.e. 30+ hours and at least 4 days in the office per week);
- (d) not currently pregnant;
- (e) predominant worksite occupation being seated office work;
- (f) not currently using a sit-stand workstation at their primary desk location at work;
- (g) willing to have a sit-stand workstation installed at their desk; and
- (h) willing to be randomized to either study arm.

### 5.3. Participant Eligibility Survey

An online eligibility survey will be distributed to each worksite employee following the informational sessions. All eligible participants will be invited to schedule a 30-minute slot during an assessment morning held at the worksite.

### 5.4. Consent

Those who are eligible and choose to attend the baseline assessment visit will be sent a copy of the consent form will be sent in advance and reviewed in person prior to commencing the visit. If the participant agrees to take part, they will provide written consent. Note: Participants from Minnesota government worksites will also be asked to sign a Tennessen agreement.

## 6. Randomization

Randomization to either the *STAND+* or *MOVE+* intervention arms of the trial will be at the level of the worksite. Randomization will be stratified on the three sectors nested within each of the two regions (Phoenix, AZ and Minneapolis/St. Paul, MN). Within each region, eligible worksites will be enrolled in pairs matched on sector, and each matched pair will be randomized so that one is randomized to receive the *STAND+* intervention with the other receiving the *MOVE+* intervention. This scheme will ensure a balanced design by both region and sector.

Randomization will not occur until all four worksites in the recruitment wave (2 per region) have completed their baseline assessments. Therefore, a participant will be considered enrolled in the active intervention once they have consented, completed baseline assessments, and paired worksites have been randomized to study arm. Prior work by our research team has suggested that we should expect 40%–75% participation within the identified worksite, which based upon worksite size will approximate our target recruitment of N = 720 participants.

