on geographical location so that we will not have any confounding by geographical location (AZ vs. MN). We will identify six pairs of sites in AZ and six pairs in MN, with the pair members having the same sector (academia, government, or healthcare/industry). Each pair will be randomized so that one worksite in each pair is assigned to the *MOVE+* intervention and the other in that pair assigned to the *STAND+* intervention. One of the site PIs and a Biostatistician at the University of Minnesota will be responsible for the randomization. Randomization will occur immediately following the baseline data collection for both sites. The PI will notify the biostatistician when there are two matched worksites ready for randomization. The two worksites will be ordered as “First” and “Second” depending on the calendar dates of the baseline data collection. The statistician, with no knowledge of the worksites, will use a coin flip to assign the two worksites to the *STAND+* or *MOVE+* interventions. Initial analyses will provide descriptions of the baseline frequencies and means (SD) of characteristics by worksite and by experimental condition. Statistical testing of differences in baseline characteristics is not necessary, but will provide assurance that the randomization has not produced a grossly unbalanced assignment. If the distributions of our outcome variables are not normally distributed, we will log-transform the outcome data. Our primary hypotheses will be tested by invoking a repeated-measures hierarchical linear model of the experimental contrast between the two conditions of the 12-month measure of LPA (min/ 8-h) and sitting (min/8-h), respectively. Because total time is standardized to 8 h, we will also express our outcomes in percent of time in LPA and sitting. A repeated measures hierarchical analysis will be conducted. The covariates expected to include are age, sex, body mass index, and the baseline values of the dependent variables (e.g., sitting time, LPA, and metabolic risk score). The resulting estimate and its standard error provide a t-statistic based on  $2(g-1)$  degrees of freedom (df), where g represents the number of worksites per experimental condition [54]. A similar analysis will examine the secondary hypothesis for the metabolic risk score. Other outcomes, including sit-stand transitions, will use hierarchical generalized linear models with a log link. The analysis approach for process (3 month) and maintenance (24 month) outcomes will be similar. In terms of missing data, sensitivity to member-dropout is small; if on average only 85% are followed, the detectable effect sizes increase by a factor 1.05. Worksite dropout would be a major threat to validity, but that is highly unlikely to occur. Baseline characteristics of those not providing follow-up data will be examined to assess whether these are non-informative missingness. Under the assumption that dropout is not related to the measures that would have been collected, the analysis of the data excluding dropouts is unbiased.

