
### 12.2 Power Analysis

We aim to enroll 24 worksites ( $N=12$  per condition) evenly distributed across Arizona and Minnesota with on average 30 employees per worksite (Total N members = 720 employees). In a baseline-adjusted analysis, let D represent the minimal detectable intervention effect, g the number of worksites per experimental condition, m the average number of members per worksite,  $S_2$  the member variance,  $T_2$  the work-site level variance,  $r_m$  and  $r_g$  the member and work-site correlations over time respectively, and  $t(d, a/2)$  and  $t(d, p)$  the critical t-statistic values based on d df for  $a/2$ =Type I alpha level (2-sided) and  $p$ =power. Then the minimal detectable difference is  $D_2 = (t(d, a/2) + t(d, p))^2 (S_2(1 - r_{2m})/m + T_2(1 - r_{2g}))^2 / g$ . Dividing by  $S_2$  yields the square of the Effect Size (ES) and  $T_2/S_2$  is the variance components ratio (VCR). In the unlikely

situation where the  $g$  are unequal, replacing  $2/g$  by  $(1/g_0+1/g_1)$  will lead to a minimal increase in  $D$  unless the  $g$  are grossly unequal. With  $g=12$  (worksites per condition),  $d=22$ , and  $N=720$ ,  $m=30$ ;  $\alpha/2$  is set to 0.025 and power is set 80%. The detectable effect sizes for this trial range from 0.21 to 0.26 across the three outcomes, which are relatively small effects, and thus we are well powered in this study. On an absolute scale, as also shown in the table, we will be able to detect a difference between intervention arms as small as 12.2 min/8-hr work day of LPA and 14.6 min/8-hr work day of sitting time. Our preliminary studies clearly demonstrate our ability to achieve these effects: (a) For LPA; the crossover study (12) showed a 38.4min/8-hr workday increase (other two studies did not target LPA or did not use a monitor designed to detect LPA); (b) for sitting, both the crossover and natural experiment showed >30min/8-hr workday reductions; and (c) for cardiometabolic risk, all 3 studies showed moderate to large effect sizes. This study is powered well to detect effects that are considerably smaller than what we have observed in our preliminary studies

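### Do the stated worksite sizes and participation rates fall short of 720 participants and so undermine the detectable differences of 12.2 and 14.6 minutes?

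*Combined protocol and SAP*

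**What the plan says.** Four places in the combined protocol and SAP bear on the expected number of participants.

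- Section 1 (Introduction) describes worksites of "small to moderate size (20–50 employees enrolled; N=720 employees across the 24 sites").
- Section 4.3, criterion (a), admits a "small to moderate size worksite (20-60 employees"). This counts all employees at the site, not those enrolled.
- Section 6 expects 40% to 75% of employees to take part, "which based upon worksite size will approximate our target recruitment of N = 720 participants".
- Section 12.2 (Power Analysis) begins "We aim to enroll 24 worksites", with "on average 30 employees per worksite (Total N members = 720 employees"). For 12 worksites per arm, 22 degrees of freedom and 80% power, it gives effect sizes of 0.21 to 0.26 and differences "as small as 12.2 min/8-hr work day of LPA and 14.6 min/8-hr work day of sitting time".

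On incomplete follow-up, Section 12.1 says that "if on average only 85% are followed, the detectable effect sizes increase by a factor 1.05". Sections 4.5 and 4.6 describe a survey of employee interest and likely participation, and a site goes forward only if that interest is sufficient. No mean worksite size, mean participation rate or numerical interest threshold is given.

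**The concern.** Section 6 presents 720 as what worksite size and participation will roughly produce, but shows no calculation. The obvious check uses the middle of each range, which gives 23 participants per site rather than 30. The power statement uses 30. If enrolment came in at 23, the trial would have less than 80% power for the differences it quotes, and a null result could be read as ruling out effects it had a fair chance of missing.

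The Introduction adds to the doubt. Size times participation gives 8 to 45 enrolled per site, not 20 to 50. At the expected rates, 50 cannot be reached, and a site with fewer than 27 employees cannot enrol 20.

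**Working it through.** **Inputs.** 24 worksites, 30 members per site, 22 degrees of freedom, 80% power, 12.2 and 14.6 min (Section 12.2); 20 to 60 employees (Section 4.3); 40% to 75% participation (Section 6); factor 1.05 at 85% follow-up (Section 12.1).

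**1. The plan's total.** 24 × 30 = 720. This reproduces.

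**2. What the ranges allow.** N = 24 × size × participation.

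| Mean size | Participation | Per site | N |
|---|---|---|---|
| 20 | 40% | 8 | 192 |
| 40 | 57.5% | 23 | 552 |
| 60 | 40% | 24 | 576 |
| 40 | 75% | 30 | 720 |
| 52.2 | 57.5% | 30 | 720 |
| 60 | 50% | 30 | 720 |
| 60 | 75% | 45 | 1,080 |

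So 720 lies inside the range, but it needs size, participation or both to average above the midpoint. At 40% participation it would need 30/0.40 = 75 employees per site, above the limit of 60.

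**3. The Introduction's range.** 60 × 75% = 45 and 20/0.75 = 26.7, which gives the two mismatches noted above. The 40% to 75% is an expectation and not a limit, however: 50 of 60 would be 83%. The same midpoint device applied to 20 to 50 enrolled gives 35 per site, or 24 × 35 = 840, which is above target.

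**4. Effect of a smaller number per site.** The detectable difference is proportional to the square root of (member term / m + worksite term). The variance components and correlations are not in the available text, so 12.2 and 14.6 cannot be rebuilt from first principles. The plan's own factor of 1.05 does fix the member share of the variance at m = 30:

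share = (1.05² − 1) / (1/0.85 − 1) = 0.1025 / 0.1765 = 0.58.

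Rounding of 1.05 (1.045 to 1.055) allows 0.52 to 0.64. At m = 23:

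factor = √[1 + 0.581 × (30/23 − 1)] = √1.177 = 1.085 (1.076 to 1.093 with rounding).

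- LPA: 12.2 × 1.085 = 13.2 min.
- Sitting: 14.6 × 1.085 = 15.8 min.
- Upper bound, with no between-worksite variance: √(30/23) = 1.142, giving 13.9 and 16.7 min.

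**5. Power for the stated differences.** At m = 30 the noncentrality is t(22, 0.975) + t(22, 0.80) = 2.932. Dividing by 1.085 and using the noncentral t with 22 degrees of freedom gives 73%. At the upper bound it is 69%.

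**6. Incomplete follow-up.** At m = 30 the disclosed factor gives 12.2 × 1.05 = 12.8 and 14.6 × 1.05 = 15.3 min. Applying 85% follow-up to m = 23 as well leaves 19.55 per site, a factor of 1.145, and 14.0 and 16.7 min with 69% power.

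**The case for a change.** The strongest form of the concern is that 720 needs favourable averages and the plan gives no reason to expect them. If sizes and rates were independent and uniform over their ranges, N would average 552, with a 95% range of 478 to 629, and would almost never reach 720. The plan's comfort from preliminary effects of 38.4 min (LPA) and more than 30 min (sitting) is also weaker than it looks. Those are reported as an increase and as reductions, whereas this trial compares two active arms, both aiming for 30 min more LPA a day, so the difference between arms could be much smaller.

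Part of this stands. The averages behind 30 per site are not stated, and the preliminary effects do not translate directly into a contrast between arms. But the uniform model has no basis in the documents. Sites are not random draws from the ranges: they are surveyed for likely participation and taken forward only if interest is sufficient, which favours higher uptake. The point about the preliminary effects concerns how large a true difference to expect. It applies equally at m = 30, and an increase of 1.0 to 1.2 min in the detectable difference does not settle it.

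The 14.0 and 16.7 min figures combine an assumed enrolment shortfall with a follow-up loss that Section 12.1 already discloses, so they are not evidence of an undisclosed error.

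**Conclusion.** No change to the plan follows. It has not been shown that the criteria fail to deliver 720, because that conclusion needs two midpoints the plan never states. Nor has it been shown that 12.2 and 14.6 min are too small, because they are given expressly for 30 per site and 720 in total.

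If enrolment did average 23 per site, the detectable differences would be about 8% larger (13.2 and 15.8 min; at most 13.9 and 16.7). The loss is modest because the 24 worksites and 22 degrees of freedom are unchanged. These figures rest on the illustrative midpoint and on the rounded factor of 1.05. The primary test uses the observed estimate and its standard error, so the precision actually achieved will show in the result whatever enrolment was forecast.

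Two blemishes remain: the averages behind 30 per site are unwritten, and the Introduction's 20 to 50 enrolled sits loosely beside the 8 to 45 implied by Sections 4.3 and 6. Both are matters of missing or untidy detail that change no result. A higher size cap would trade against the aim of studying small to moderate worksites. A criterion based on expected enrolment would largely formalise the interest screen already in Sections 4.5 and 4.6.

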## 7. Study Interventions

### 7.1 Intervention Overview

The ‘Stand & Move at Work’ interventions will be delivered over 12 months and is based upon both the social ecological framework and social cognitive theory principles. The intervention development team is comprised of behavioral scientists, exercise scientists, ergonomists, and worksite wellness coordinators. The primary behavioral target of the *MOVE+* intervention is to

accumulate 30 min or more additional LPA each day. The primary behavioral target of the *STAND+* intervention is, in addition to the *MOVE+* target, to increase time spent standing to 50% of desk-based time during the workday (e.g. standing for 3 h out of 6 total desk-hours per day).

Our approach will target intervention strategies at the individual, social, environmental, and organizational levels.

All intervention materials will be manualized into the Stand & Move at Work “Toolkit.” The toolkit will be distributed to each worksite prior to the intervention start date. It is expected that each worksite and/or sector may differ in the time, resources, space, and personnel available to dedicate to the implementation of the intervention. The Toolkit will therefore be comprised of both “required” strategies (i.e., strategies that are required to be implemented by worksite staff during the intervention period) and “optional” strategies (i.e., strategies that worksite staff are encouraged to implement as are appropriate given the worksite context). Additional strategies generated by the worksite staff will also be encouraged. This approach ensures uniformity of the delivered interventions across worksites and allows flexibility and autonomy among worksites. Actual implementation of intervention strategies will be closely monitored through quarterly worksite audits and worksite leader interviews.

To help facilitate these changes within the worksite, trained research staff met with worksite advocates quarterly to discuss implementation strategies for the upcoming quarter, as well as successes and barriers of implementation of the previous quarter. The worksite leader holds a higher level management position to which the department, division or unit employees report. This person will not be required to implement changes but will voice support, encourage participation and approve policy changes. Worksite advocate(s) plays an active role with program participants and will work to implement the selected changes. Considered a primary contact to link worksite employees and management. Advocate characteristics include: outgoing, ability to connect and engage with others, regular interaction with staff, good communicators.

